10.3.3 Secondary outcome analysis

- Different sensitivity analyses will be done to evaluate the treatment effect at 6 weeks. Confounders like the use of rescue medication, the 3 stratifying variables (sensory disturbances such as hyperalgesia/allodynia, spontaneous positive sensory disturbances and duration of pain) and some other known confounders (gender, level of education, family situation) will be added to the linear regression model.
 - A linear mixed model using all quality of life measurements over the 26 weeks with subject as random effect will improve the precision on the estimated treatment effect at 6 weeks. This complex model will be expanded by including site as a random effect and possible confounders will also be added to this model as fixed effects. From the linear mixed model the long term profiles of the treatments over the 26 weeks can be determined and using time as a categorical variable in this model will allow different linear evolutions from one time point to another.
- For each patient, an area under the curve including all quality of life
 measurements will be calculated using the trapezium rule and compared
 between the different treatment arms using linear regression. The area under
 the curve can be seen as a summary measure summing up initial treatment
 response or lack off and the effect of any rescue medication during follow-up.
- A similar analysis will be done for the subgroup of patients who adhered to the protocol in a per protocol analysis.
- Linear regression at 6 and 26 weeks will be performed to compare the pain intensity between the 3 treatment arms. Changes over time will be analyzed using linear mixed effect models.
- The use of rescue medication using MQS-III will be evaluated at 6 and 26 weeks using linear regression. Changes over time will be analyzed using linear mixed effect models.
- The time to worsening will be studied in a time-to event analysis comparing the different treatment arms. Two different events of worsening will be considered:
 - The first time the patient experiences a 30% increase in MQS-III score
 - This implies that patient has either significantly increased the use (number of intakes) of the rescue medication or has started taking analgesics of a higher level (WHO step ladder)
 - The first time the patient has a worsening of the pain in terms of 2 units rise on the pain intensity (numeric rating scale NRS) scale compared to the previous assessment.
- The percentage of systemic drug-related side effects will be evaluated at 6 and 26 weeks using Chi-square test or Fisher's exact test. The evolution of the percentage of systemic drug-related side effects over time will be analyzed using a generalized linear mixed effects model using the clinical visit data and

the self-reported patient data.

- Discontinuation of study drug or study withdrawal: the percentage of study
 withdrawal will be compared after 6 and 26 weeks with a Chi-square test or
 Fisher's exact test whatever is appropriate based on assumptions. The time to
 discontinuation will also be studied in a time-to event analysis comparing the
 different treatment arms. The self-reported patient data will be used for this.
- Global perceived effect (GPE), effect on mood (Hospital Anxiety and Depression Scale), quality of sleep (Sleep-NRS and ISI), participation in activities (Utrecht Work Engagement Scale-9), impact of pain on functioning (interference – BPI), and Work Productivity and Activity Impairment (WPAI-Neuropathic Pain) will be compared at 26 weeks using linear regression and over time using linear mixed models.
- Similar to the primary outcome the treatment effect on the secondary outcomes will be estimated in a model with adjustment for confounders and including site as a random effect

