3.5 Secondary endpoints

- Long term quality of life profile;
- Reduction in pain intensity (PI-NRS);
- Time to worsening of the pain and use of rescue medication for pain (MQS III-R);
- Global perceived effect (GPE);
- Effect on mood (Hospital Anxiety and Depression Scale);
- Quality of sleep (NRS and ISI);
- Percentage of patients without systemic drug related side effects (dizziness, fatigue, vertigo, somnolence, headache, blurred vision);
- Time to discontinuation of the study drug and proportion of patients stopping the drug;
- Participation in activities (Utrecht Work Engagement Scale-9);
- Impact of pain on functioning (interference BPI);
- Work Productivity and Activity Impairment (WPAI: Neuropathic Pain, v2.2, Belgium);
- Neuropathic Pain Symptom Inventory (NPSI).

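### The week-6 sensitivity regression adjusts for rescue-medication use, which the protocol otherwise treats as an outcome of treatment; with on-treatment use it would not estimate the intention-to-treat effect

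*Protocol*

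**What the plan says.** Only the protocol was available; a separate SAP may exist but was not seen.

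- **Primary model (10.3.2).** EQ-5D-5L at week 6 is regressed on treatment and baseline quality of life, by intention to treat. There is no rescue term.
- **Sensitivity analyses (10.3.3).** "Different sensitivity analyses will be done to evaluate the treatment effect at 6 weeks". The covariates to be added begin with "Confounders like the use of rescue medication, the 3 stratifying variables" and continue with gender, education and family situation.
- **Mixed model (10.3.3).** This model is meant to sharpen the week-6 estimate, and "possible confounders will also be added to this model as fixed effects". The confounders are not listed.
- **Secondary outcomes (10.3.3, last item).** The treatment effect "will be estimated in a model with adjustment for confounders and including site as a random effect". Again there is no list.
- **Rescue use as an outcome.** Section 3.5 lists "Time to worsening of the pain and use of rescue medication for pain (MQS III-R") as a secondary endpoint. Section 10.3.3 adds: "The use of rescue medication using MQS-III will be evaluated at 6 and 26 weeks using linear regression". A 30% rise in MQS-III is one of the two events that define worsening. The area-under-the-curve analysis is described as taking in "the effect of any rescue medication during follow-up".
- **Baseline measurement (7.6).** MQS III is also collected before randomisation, but 10.3.3 does not name that score as the covariate.

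**The concern.** A confounder of a randomised comparison would have to precede allocation, and randomisation already deals with those. Rescue use during treatment comes after allocation. It can be changed by the allocated treatment, it may itself affect quality of life, and it shares causes with quality of life, such as underlying pain severity. Conditioning on it does two things: it takes out whatever part of the treatment effect runs through rescue use, and it can induce an association between arm and unmeasured severity. The resulting coefficient is not the total effect that 10.3.2 targets.

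At stake is the value of the robustness check. A sensitivity analysis is informative when it estimates the same quantity under different assumptions. If the adjusted estimate shrinks, a reader cannot tell whether the primary result is fragile or whether the model has removed part of a real effect. If it holds, that is not clear support either. The trial is open label with patient-reported outcomes, so readers will look at these checks.

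**Working it through.** **Step 1. The plan's own figure.** Inputs from section 10.1: effect 0.08, SD 0.240, alpha 0.05/2 = 0.025 (two-sided assumed), power 80%. Normal approximation: n = 2 × (2.241 + 0.842)² × 0.240² / 0.08² = 2 × 9.505 × 9 = 171.1, so 172 per arm. The exact t-test gives 172.35, so 173, as stated. With 12% drop-out, 173 / 0.88 = 196.6, so 197 per arm and 3 × 197 = 591. The sample size reproduces and does not depend on this point; 0.08 serves below only as the yardstick.

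**Step 2. Which rescue use is meant?** The covariate sentence gives no time point. Every other mention of rescue use in 10.3.3 is on-treatment: the comparison at weeks 6 and 26, the 30% rise as an event, and its role in the area under the curve. Section 6 likewise expects MQS-III to move with analgesic intake as the trial proceeds. On-treatment use is therefore the natural reading, but it is not fixed.

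**Step 3. What adjustment does.** In a linear model,

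adjusted effect = total effect − a × b,

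where a is the arm difference in rescue use (in SD units, topical minus pregabalin) and b is the within-arm coefficient of rescue use on EQ-5D-5L. The shift is zero if a = 0 or b = 0. The protocol gives neither value.

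**Step 4. Size under assumed inputs.** Assume |a| = 0.1 to 0.5 SD, a within-arm correlation of absolute size r = 0.2 to 0.5, and |b| = r × 0.24. The 0.24 is the SD of change from 10.1; a model that includes baseline would need the baseline-adjusted coefficient, so this is a rough scale only.

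- Smallest: 0.1 × 0.2 × 0.24 = 0.0048, which is 6% of 0.08.
- Middle: 0.3 × 0.3 × 0.24 = 0.0216, which is 27%.
- Largest: 0.5 × 0.5 × 0.24 = 0.060, which is 75%.

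If topical patients use less rescue and rescue use goes with worse EQ-5D-5L, a × b is positive and the estimate falls, to between 0.075 and 0.020. If one of the two signs is reversed, it rises by the same amount.

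**Step 5. Simulation check.** Two arms, true total effect 0.080, SD 0.24, 2,000,000 simulated patients per run. Where unmeasured severity acts on EQ-5D-5L, it does so at −0.07 per SD; its loading on rescue use is 0.5. All of these are assumed inputs.

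| Arm difference in rescue use (SD) | Direct effect of rescue on EQ-5D-5L per SD | Severity acts on EQ-5D-5L | b | Adjusted effect |
|---|---|---|---|---|
| 0 | −0.05 | yes | −0.085 | 0.080 |
| −0.4 | −0.05 | no | −0.050 | 0.060 |
| −0.4 | −0.05 | yes | −0.085 | 0.046 |
| −0.4 | 0 | yes | −0.035 | 0.066 |
| −0.4 | +0.03 | yes | −0.005 | 0.078 |
| −0.4 | +0.03 | no | +0.030 | 0.092 |
| −0.6 | +0.03 | no | +0.030 | 0.098 |

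Each row agrees with the identity in step 3; for example, 0.080 − (−0.4 × −0.085) = 0.046. The fourth row shows a shift with no causal effect of rescue use at all, through shared severity alone.

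**The case against.** The strongest reply has four parts.

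- **The covariate may be the baseline score.** All the other listed covariates are known before randomisation, MQS III is measured then, and covariate timing can be left to a SAP. This reading is possible and would remove the problem. It is not stated, though, and it runs against the other uses of the term in 10.3.3. If it is what was meant, the sentence still needs one word to say so.
- **Only sensitivity analyses are touched.** This stands. A reader might infer that the primary result is biased, but the documents do not support that: the model in 10.3.2 contains treatment and baseline quality of life only, and nothing lets a sensitivity analysis override it. The area-under-the-curve comparison is also described without covariates.
- **The spread to other models is inferred.** A reader might conclude that every adjusted model carries the rescue term. The mixed model and the secondary-outcome models refer to confounders without listing them. The shared word suggests the same set, but does not establish it. If the set is the same, the MQS-III outcome would be adjusted for rescue use, and so appear on both sides of its own model.
- **Any percentage loss is assumed.** This also stands. A reader might take the adjustment to remove a known share of the effect, but the protocol has no figure for the arm difference or for the correlation, and the shift can be nil or upward.

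One further strong reading should be resisted. Section 8.1 labels gabapentin as rescue medication, and it is the alternative offered in the pregabalin arm. On that meaning the covariate would come close to marking the arm. Section 10.3.3, however, measures rescue use by MQS-III, which covers analgesics in general, so the text does not support taking gabapentin as the covariate.

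**Conclusion.** The point holds for the week-6 sensitivity regression, as something that should be fixed. As written, the protocol labels as a confounder a variable that it elsewhere analyses as an outcome of treatment. If on-treatment use is entered, the coefficient does not estimate the total intention-to-treat effect and cannot confirm or question the primary result.

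The size is open. It is zero if the arms do not differ in rescue use, or if rescue use is unrelated to EQ-5D-5L given arm. The protocol plans to examine that arm difference, so its absence cannot be presumed. Under the assumed inputs above, the shift runs from 0.005 to 0.060 against 0.08, in either direction. The primary analysis and the sample size of 591 are unaffected. The mixed model and the secondary-outcome models are affected only if their unlisted confounders include rescue use, as the wording suggests but does not say.

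**What to change.** In section 10.3.3:

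1. Replace use of rescue medication in the covariate list with the baseline MQS-III score.
2. State that covariates in all adjusted models (the week-6 regression, the mixed model and the secondary-outcome models) are restricted to variables measured before randomisation.
3. Keep on-treatment rescue use as an outcome only. If its influence on the week-6 effect is of interest, define a separate supplementary analysis with its own stated target, and do not call it a sensitivity analysis of the intention-to-treat effect.

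The cost is a sentence or two in the protocol, repeated in any SAP. The baseline score is already collected, and neither the data collection nor the sample size changes. The edit should be made before any comparison between arms is seen, so that dropping the term cannot look driven by results.

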2.1 Assessment and management of risk

This study should be considered as a **low-intervention clinical trial**, based on the risk assessment at the clinical trial level. Part of the proposed use of the therapies in this study is off label use but well established in international literature. However this study does not meet the criteria to obtain a pilot label exemption rule by the FAGG.

The investigational medicinal products are authorised and used in accordance with the terms of the marketing authorisation, with the exemption of the lidocaine plaster that has only a marketed authorisation for postherpetic neuralgia (PHN). Their application in neuropathic pain syndromes is furthermore evidence-based and supported by published scientific evidence on the safety and efficacy of these investigational medicinal products.

The study will be performed in recognized Multidisciplinary Pain Centers (MPC), that are all familiar with the neuropathic pain conditions which are investigated, the therapeutic approach to these conditions and the specific handling of the investigated medicinal products.

In the years to come (2018-2020) there will be no major competing trial(s) to be expected in the field of localized neuropathic pain syndromes, since no innovative treatment options are currently in an immediate pre-clinical stage of development.

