7.6 Baseline data (pre-randomisation, to be collected before randomisation)

The baseline data will be collected between one week before day 0 and at least 48 hours before day 0 through the online system. Baseline data will be collected in all cases before the patient is randomised and starts the treatment. The researcher will be able to check the completion of the baseline data in the online system.

Baseline status (V1) on the following variables (*measurements belonging to standard care are indicated in bold*):

- Health-related quality of life (EQ-5D-5L)
- Medication use (MQS III Medication Quantification Score)
- Pain using PI-NRS (pain intensity) and NPSI (Neuropathic Pain Symptom Inventory)
- The Pain Intensity Numeric Rating Scale (PI-NRS) is an 11-point scale for patient self-reporting of pain
- The Neuropathic Pain Symptom Inventory (NPSI) is a 12-item patient reported outcome measure that contains 10 descriptors representing 5 dimensions of pain (burning pain, deep/pressing pain, paroxysmal pain, evoked pain and paresthesia/dysesthesia) and 2 temporal items designed to assess pain duration and the number of pain paroxysms
- Quality of life of the patient using several questionnaires: Insomnia Severity Index (ISI), quality of sleep (NRS), HADS (Hospital Anxiety and Depression Scale)
- The Insomnia Severity Index (ISI) is a validated seven-item patient questionnaire used to quantify insomnia severity
- The Hospital Anxiety and Depression Scale (HADS) is a self-rated questionnaire to detect states of depression, anxiety and emotional distress
- Functional status of the patient using several questionnaires: Interference BPI (impact of pain on functioning), Utrecht Work Engagement Scale-9 and WPAI (Work Productivity and Activity Impairment)

Demographics will be collected at the time of the screening where the following variables are considered important (all belonging to standard clinical care): age, gender, level of education and family situation.

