10 STATISTICS AND DATA ANALYSIS

10.1 Sample size calculation

The primary outcome is the change in EQ-5D-5L from baseline to 6 weeks.

In the paper of Baron et al (2009) they evaluate the short-term effect of 5% lidocaine medicated plaster versus pregabalin on the quality of life.⁵⁸ Baron et al. reported 0.12 (0.240) as the mean change (SD) for EQ-5D from baseline to 4 weeks in the 5% lidocaine medicated plaster group compared to 0.04 (0.235) in the pregabalin group or an effect of 0.08. According to Walters and Brazier (2005) the mean minimally important clinical difference (MICD) for the EQ-5D is 0.074 for all patient groups and 0.081 for the backpain patient group.⁵⁹ **We have therefore powered the study around this effect of 0.08.**

Based on these numbers we would need **173 patients per treatment arm** using an independent samples t-test to have 80% power to detect an effect of 0.08 assuming a standard deviation of 0.240 with an alpha of 0.05/2. We are interested in all 3 comparisons, between on one hand the systemic versus the topical treatment options (pregabalin versus capsaicin 8% patch, pregabalin versus lidocaine 5% patch), and on the other hand within the topical treatment options (capsaicin 8% patch versus lidocaine 5% patch - as they imply a considerable difference in cost). Given the fact that each group will be used twice in the comparisons we corrected the significance level with a factor 2 to keep the overall type I error at 5%.

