In Haanpää et al.³⁶ and Baron et al. patient completion rates for the follow-up of 90% and 96% respectively are reported which seems - bearing in mind that the burden on the patients in follow-up assessments is extremely low in the proposed pragmatic trial - realistic to us. However, in the systemic treatment arm drop-out from the study medication will be considerable (due to side effects). Indeed, in Baron et al. 39 of 153 patients (25.5%) of the pregabalin group discontinued the study medication and Haanpää et al. reports 41 out of 277 (14.8%) of the pregabalin arm withdrawing from the study medication. If we combine the two studies, we get 80 out of 430 or 18.6% drop out rate. For capsaicin 8% patch the withdrawal from study medication was 6 out of 282 (2.1%) and for lidocaine 5% plaster 9 out of 155 (5.8%) withdrew. Hence, we anticipated an average drop-out rate between 5.8% and 18.6% of 12% for each treatment arm which implies 197 patients per treatment group. In total, we would need to randomize **591 patients** in a 1:1:1 way to the 3 treatment arms.

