10.3 Statistical analysis plan

10.3.1 Summary of baseline data and flow of patients

- Compare primary outcome quality of life (EQ-5D-5L) at baseline between the treatment arms. Means and standard deviations per treatment group will be reported.
- Compare pain, mood, sleep and functional status at baseline between the treatment arms using the different questionnaires (PI-NRS, Sleep-NRS, HADS, ISI, Utrecht Work Engagement Scale-9, Interference BPI and WPAI). Means and standard deviations per treatment group will be reported.
- Compare gender, level of education and family situation between the treatment arms. Proportions per treatment group will be reported.
- Compare the 3 stratifying variables hyperalgesia/allodynia (absent or not), spontaneous positive sensory phenomena (such as dysesthesia) (absent or not) and duration of pain (less than or more than 3 months) between the treatment arms. Proportions per treatment group will be reported.
- A consort flow diagram will be produced to get an overview of the number of patients available at each stage: eligibility, randomisation, allocation, discontinuation and follow-up.

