	154.26€ per patch	Budget 2: if reimbursement by RIZIV/INAMI; Up to 4 patches per patient, max. of 3 applications in each patient (every 90 days)	Maximum cost of 7.35€ per day (reimbursement category C)
Pregabalin 75mg - LYRICA	0.06€ per 75mg	Up to 8 capsules per day per patient, during 24 weeks	Maximum cost of 0.48€ per day
Gabapentin 300mg – EG	0.05€ per 300 mg	Up to 7 capsules per day per patient, during 24 weeks	Maximum cost of 0.30€ per day

The costs detailed in this table are based on the current reimbursement policies and do not take into account eventual reimbursement by RIZIV/INAMI for the patients participating in this trial.

Indirect costs associated with lost productivity at work will be calculated using the method of Lofland et al.⁷⁹, based on the Work Productivity and Activity Impairment (WPAI) scale for special health problems.^{80,81} In this protocol the WPAI scale for Neuropathic Pain will be applied (v2.2 – Belgium with validated Dutch and French translations available). Productivity will be defined as a percentage from 0% to 100% and mapped to pain scores such that for each point change in pain score, the change in lost productivity can be estimated. Costs will be estimated on mean monthly income in Belgium.

QALYs

For calculation of the cost-utility, estimates of QOL scores for determination of QALYs were based on regression equations with the pain NRS scores, age, and sex as independent variables. These values, estimated individually for males and females, were then weighted and averaged by sex ratio and average age to derive weighted averages for each NRS score.

Cost-utility

Based on QALY and costs, the incremental cost-utility ratio (ICUR) will be calculated to evaluate the cost-utility of topical treatments. Sensitivity analyses will be performed to account for uncertainties in the data sources and assumptions, and to confirm the robustness of the ICURs estimated in the base case.

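### Age, which section 7.6 calls important, is missing from the primary model, the named covariates and the baseline comparison, and no baseline summary describes etiology

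*Protocol*

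**What the plan says.** **Age.** Section 7.6 names the demographics it regards as important: "age, gender, level of education and family situation". The screening list in 7.1.2 and the table of procedures in 7.8 confirm that age is collected. The analysis sections give a shorter list:

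- 10.3.1: "Compare gender, level of education and family situation between the treatment arms", summarised as proportions. No other item in that section covers age.
- 10.3.2: the primary model contains treatment and baseline EQ-5D-5L, and nothing else.
- 10.3.3: the adjusted sensitivity models take rescue medication, the three stratifying variables and "some other known confounders (gender, level of education, family situation").

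Section 10.5, on the possible cost-utility analysis, derives quality-of-life scores from "regression equations with the pain NRS scores, age, and sex as independent variables".

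**Etiology.** The title and the primary objective in 3.1 define the population by its mixed etiologies, and section 6 presents unrestricted etiology as a feature of the pragmatic design. Section 2.1 notes an exception to on-label use for the "lidocaine plaster that has only a marketed authorisation for postherpetic neuralgia (PHN"). Etiology is not among the minimisation factors (7.3), the baseline comparisons (10.3.1), the named covariates (10.3.3) or the interaction tests (10.3.5), which use only the three stratifying variables.

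**The concern.** The protocol gives the same demographic list in three places, and age is in the first but not in the other two. Nothing in the text suggests that this was intended. Age is a baseline value already in hand and plausibly prognostic for a quality-of-life score, so adjusting for it carries almost no cost. Section 10.3.2 fixes the primary model in the protocol, so leaving age out there is a choice made in this document and not a detail left to a statistical analysis plan.

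For etiology the stake is description. The result will be an average over whatever mix of conditions is recruited. A reader who wants to know to whom it applies, or how many lidocaine patients fell within the licensed indication, needs that mix by arm. The planned analyses do not say it will be shown.

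**Working it through.** **1. The plan's own sample size.** Inputs from 10.1: "80% power to detect an effect of 0.08 assuming a standard deviation of 0.240 with an alpha of 0.05/2". I take alpha = 0.025 as two-sided.

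- Normal approximation: n = 2 × (0.24/0.08)² × (2.241 + 0.842)² = 171.1, so 172 per arm.
- Exact two-sample t-test: 172.35, so 173. This matches "173 patients per treatment arm".
- Drop-out: "we anticipated an average drop-out rate between 5.8% and 18.6% of 12% for each treatment arm". 173/0.88 = 196.6, so 197 per arm, and 3 × 197 = 591.

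The stated figures reproduce and are not in question.

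**2. What age could add to the primary comparison.** The documents give no figure for the variance in 6-week EQ-5D-5L that age explains beyond baseline EQ-5D-5L. Call it R² and assume 0 to 5%. Take 0.24 as the residual SD before age is added (also an assumption, since 0.240 is the SD of a change score in the cited study). Then SD = 0.24 × √(1 − R²). Power is for 173 per arm, difference 0.08, alpha 0.025.

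| Assumed R² | Residual SD | Fall in standard error | Power | n per arm for 80% |
|---|---|---|---|---|
| 0% | 0.2400 | 0% | 80.2% | 173 |
| 1% | 0.2388 | 0.5% | 80.6% | 171 |
| 2% | 0.2376 | 1.0% | 81.0% | 169 |
| 5% | 0.2339 | 2.5% | 82.3% | 164 |

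The gain is at most about two power points over this range and may be nil.

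**3. What a split by postherpetic neuralgia (PHN) could show.** The etiology mix is not given. Assume 30% PHN, so 173 × 0.3 = 51.9 and 173 × 0.7 = 121.1 patients per arm, for one pairwise comparison.

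- Effect within PHN: SE = 0.24 × √(2/51.9) = 0.047, 95% half-width 1.96 × 0.047 = 0.092.
- Effect outside PHN: SE = 0.24 × √(2/121.1) = 0.031, half-width 0.060.
- Difference between the two: SE = 0.24 × √(2/51.9 + 2/121.1) = 0.056, half-width 0.110.
- Power for an interaction of 0.08 at two-sided 0.05: about 30%. With assumed shares of 20% and 50% it is about 24% and 34%.
- Interaction detectable with 80% power: 0.158 at a 30% share (0.181 at 20%, 0.145 at 50%), roughly twice the target effect.

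Such a display can describe the two groups but cannot decide whether they differ.

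**The case against.** Several points on the other side have force.

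- **The covariate lists are open.** Section 10.3.3 introduces its confounders as examples, and its mixed model allows further ones to be added. A reader might infer that age and etiology are shut out of the adjusted models. The text does not say so: they are unnamed, not excluded, and an analysis plan could add them. This stands. It does not reach 10.3.2, where the primary model is closed.
- **A baseline table would normally show age anyway.** The sentence in 10.3.1 deals with categorical variables, and age is continuous. That may explain the omission, but 10.3.1 also lists continuous measures with means and standard deviations and does not put age there. The gap is small and easily filled.
- **The primary model already has the covariate that matters most.** It adjusts for baseline EQ-5D-5L, so anything age adds is a remainder of unknown size. This stands, and it is why the assumed range must include zero.
- **Section 10.5 is weak support.** Its regression converts pain scores into quality-of-life values for an economic analysis that may not be done. It shows that the authors relate age to quality of life; it does not contradict 10.3.3.
- **The choice of effect modifiers is reasoned.** The rationale and the exploratory objective concern sensory phenotype, and the interaction tests follow from that. Nothing here argues for replacing them.
- **Etiology may well be recorded.** Screening takes relevant history and current condition. The case report form is not at hand, so it cannot be said that the information will be missing.

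**Conclusion.** The point holds as a minor, nearly free improvement. Section 7.6 and the analysis sections disagree about age, the fixed primary model omits it, and no baseline summary is planned for the characteristic that defines the population.

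The gain in precision is small and rests on assumption: for R² of 0 to 5%, the standard error falls by 0 to 2.5% and power goes from about 80% to at most about 82%. The documents support no firmer figure.

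Two stronger readings should be resisted. A reader might infer that without etiology in the model the trial has no basis for a conclusion in a mixed population. In 3.1 the reference to varied etiologies describes who is studied, and randomisation supports the average effect in that population; no claim is made that the effect is the same in each condition. A reader might also infer that a PHN-by-treatment test would settle whether the result holds inside and outside lidocaine's licensed indication. With an interaction standard error of about 0.056 and about 30% power at an assumed 30% share, it would not, and the licensing question does not bear on pregabalin versus capsaicin.

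**What to change.** - **10.3.2:** add age, as a continuous covariate, to the primary model beside baseline EQ-5D-5L.
- **10.3.3:** add age to the named covariates so that the list agrees with 7.6.
- **10.3.1:** report age (mean, SD) and etiology in a few groups defined in advance (proportions) by arm, with etiology taken from the recorded medical history.
- **Optional, in 10.3.5:** show treatment effects with confidence intervals by PHN yes/no, labelled as a descriptive display and not a test.

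The change to 10.3.2 alters protocol text and should be made, with its date, before any outcome data are compared by arm. The rest is wording in the protocol or the analysis plan. If etiology is held only as free text, someone must group it from the medical history without reference to outcome. Age is already collected, and the sample size stays at 591.
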